| Design | This is a randomized, double-masked, placebo-controlled study to determine the safety of pAF in patients who undergo PRK. |
| Study Duration | Two years |
| Study Center(s) | Single Center-John A. Moran Eye Center |
| Objectives | 
Primary Objectives:
 
• To determine the safety of using processed Amniotic Fluid (pAF) in patients following PRK. 
Secondary Objectives:
 
• To determine if pAF hastens re-epithelialization following PRK compared to placebo.• To determine if pAF reduces post-operative pain following PRK compared to placebo.• To determine if pAF affects visual outcome following PRK compared to placebo.• To determine if pAF affects ocular surface staining and corneal regularity following PRK compared to placebo. |

Continued on next page

Continued from previous page

| | |
|---|---|
| Number of Subjects | 63 patients |
| Diagnosis and Main Eligibility Criteria | 
Inclusion:
 
 1. Patients aged 21 years and older. 2. Patients undergoing PRK for visual correction in both eyes. 3. Willing and able to give consent for study participation and comply with study procedures, including follow-up visits. 
Exclusion:
 
 1. Patients with any active eye disease, including keratoconus or any other ectatic disorders. 2. Patients with documented uncontrolled diabetes. 3. Patients with severe dry eye as measured by corneal staining. 4. Patients with calculated PRK treatment resulting in residual stromal bed <300 um. 5. Patients who have had previous eye surgery or refractive laser procedures. 6. Patients with any active collagen vascular disease. 7. Patients who do not have potential of 20/20 or better best-corrected vision in each eye. |
| Study Product, Dose, Route, Regimen | 
Individual patients will be randomized to one of two post-operative drop regimens, control eyes that will receive placebo saline solution (NaCl 0.9%, Baxter Medical), and study eyes that will receive pAF four times daily for seven days.
 
Both eyes of all patients will otherwise be treated with the standard post-operative drop regimen for our center. This includes moxifloxacin 0.3%, prednisolone acetate 1%, and ketorolac 0.5% on a tapering schedule. A bandage contact lens will also be placed as per standard post-PRK care.
 
All patients will be instructed to use supplemental preservative free artificial tears from individual vials (any brand) no less than 3 but up to 8 times a day for both eyes for the first 7 days.
 |

Continued on next page

Continued from previous page

| | |
|-------------------------|--|
| Statistical Methodology | Standard statistics will be calculated and used to describe the two treatment groups in terms of all study variables. Statistics will be compiled for each variable at the study time points listed in the data collection protocol. |
|-------------------------|--|

2 Objectives

Primary Objectives:

- a. To determine the safety of using pAF to improve ocular surface healing in PRK patients compared to use of placebo drops.

Secondary Objectives:

- a. To determine if pAF hastens re-epithelialization in patients following PRK compared to placebo.
- b. To determine if pAF reduces post-operative pain following PRK compared to placebo.
- c. To determine if pAF affects visual outcome following PRK compared to placebo.
- d. To determine if pAF affects ocular surface staining and corneal regularity following PRK compared to placebo.

3 Rationale and Background

3.1 Photorefractive Keratectomy (PRK)

Photorefractive Keratectomy (PRK) is a common elective surgery used to correct refractive errors (nearsightedness, farsightedness, and astigmatism). An excimer laser is used to remove stromal corneal tissue to achieve the desired refractive outcome. The corneal epithelium is removed prior to excimer laser treatment, creating a very well controlled and reproducible surgical injury to the ocular surface. Post-operative healing is easily monitored and quite predictable, but does cause potential discomfort and visual blurring for the patient, hence any supportive measures or medication that hastens epithelial healing and recovery is desirable to allow patients to regain visual function more quickly.^{1,2} In rare circumstances, the creation of these epithelial defects may also be associated with other side effects or complications including delayed epithelial healing, recurrent erosions, or dry eye. We propose that amniotic fluid

drops may be beneficial in promoting ocular surface healing following PRK. Purified amniotic fluid (pAF) contains anti-inflammatory, anti-microbial and regenerative factors similar to solid amniotic membrane.³ Amniotic membrane has growth factors and natural anti-inflammatory factors and has demonstrated therapeutic effect following a variety of ocular surface injuries or surgery including: Stevens Johnson Syndrome and pterygium removal.^{4,5} Anecdotal experience has indicated that amniotic fluid eye drops may be beneficial in graft-versus-host disease, but controlled studies are needed to determine if this has clear beneficial effects.

3.2 Amniotic fluid (AF):

Early after conception and until the mothers water breaks for the delivery of their infant, the fetus is bathed in amniotic fluid. AF functions as a supportive cushion to the fetus and provides a protective environment. AF is a rich source of nutrients, cytokines and growth factors that are required for fetal development and maturation.⁶ AF also contains stem cells with the potential to differentiate along multiple cell lineages.^{7,8} The protective and regenerative properties of AF are achieved via the exchange of water and solutes with surrounding tissues. This is accomplished via the utilization of different pathways during the course of a pregnancy that likely contribute to changes in the composition of the AF with gestational age.⁶ A report that concentrates of AF inhibited the development of peritonitis was among some of the first evidence that AF had protective biological properties.⁹ This was followed by a publication by Shimberg and co-workers that AF accelerates defense-repair mechanisms within damaged joints.^{9,10} Since these early publications, more sophisticated evaluations have revealed the presence of antimicrobial, immunomodulatory, and growth-promoting activities in AF.⁶ Reports about antimicrobial activity in AF differs¹¹ among investigators. Some studies show that AF is inhibitory, while others show no effect against the same microorganisms. Yet, other reports provide evidence that AF with low antimicrobial activity is associated with a high incidence of an infectious syndrome in pregnant women.¹² Components with antimicrobial, antiviral and antifungal activity that are present in AF include lysozyme, peroxidase, transferrin, -lysin, immunoglobulins and zinc-peptide complexes.¹¹ Immunomodulatory properties of AF are evident from studies showing that enteral feeding of AF suppresses the pro-inflammatory responses in preterm pigs with necrotizing enterocolitis.¹³ While growth promoting activities of AF are supported by animal studies as well as by in vitro studies showing that AF can enhance neochondrogenesis,¹⁴ regenerate peripheral nerves¹⁵ and bone,¹⁶ accelerate re-epithelialization in corneas,¹⁷ and promote healing of human skin wounds.¹⁸ Some of the factors that are found in AF that may contribute to these activities include inflammatory mediators that include, but are not limited to TNF-a, IL-6, IL8, and IL-10,¹⁹ trophic factors that include EGF, IGF-1, FGF, HGF and TGF-a,²⁰⁻²⁴ and HA, an important factor in promoting re- epithelialization in human skin wounds.¹⁸

Based on the hypothesis that nutrients, cytokines and growth factors contained in the non-cellular fraction of AF are useful for reparative and regenerative treatments in patients, Pierce et al conducted a study at the University of Utah to address three issues. The first was to determine the feasibility of consenting and screening volunteer donors for the routine collection of AF from full-term pregnant women scheduled for caesarean- section (C-sections) and then processing the AF for clinical applications. The second aim was to develop a processing method that resulted in a cell-free AF preparation suitable for clinical applications. The third goal was to gain a better understanding about components of AF procured from full-term pregnancies.

With the above 3 goals in mind, human AF was collected by the staff of the Obstetrical and Gynecological department at the University of Utah hospital and was processed by technical staff of the Cell Therapy and Regenerative Medicine (CTRM) facility at the University of Utah. Physician executed abdominal incisions were performed through the abdominal and uterine muscles without cutting into the amnion membrane. Using a sterile soft suction catheter connected to a sterile MediVac Suction Container (Cardinal Health, Waukegan, IL), a blunt end insertion with a catheter was made into the amnion membrane and the AF was aseptically suctioned into a MediVac Container. The container was labelled, wrapped in frozen Insul-ice mats (Fisher Scientific, Hanover Park, IL) and placed in a temperature-monitored shipper that was validated for transport between 2 and 8 °C. The AF was transported to the CTRM facility at the University of Utah. Upon arrival at the CTRM facility, the product was immediately placed into a refrigerator at 2-8 °C until processing occurred. At the time of processing, the MediVac container with AF was aseptically placed in a biological safety cabinet and the AF was transferred via aseptic techniques into sterile centrifuge tubes. The total volume and gross appearance of the AF were recorded and samples were removed for sterility testing, cell counts and other relevant testing. The AF was centrifuged at 1400Xg for 20 min at 4 °C. Once centrifugation was complete, the supernatant was expressed into a new transfer pack and the remaining cell pellet was characterized and cultured as described below. The supernatant from the AF was processed using a proprietary filtration technology to sterilize and eliminate cellular debris from the final product. AF collections and final products were evaluated for total volume, fluid chemistries, total protein, and hyaluronic acid (HA) levels. Final products of processed AF (pAF) were also assessed for their cellular content and for their protein profiles using quantitative antibody arrays.

To validate the above described approach for collecting and processing AF, 36 pregnant women consented and passed the donor screening criteria. AF was successfully collected from 17 individuals. Median AF volumes were 70 mL (range 10-815 mL; n = 17). Fluid chemistries were similar, but some differences were noted in HA levels and cytokine profiles. Cytokine arrays revealed that an average of 304 ± 20 (mean \pm SD; n=3) of 400 proteins tested were present in AF with a majority of cytokines associated with host defense. Among the 300 proteins present in pAF were two proteins with functions known to be associated with ocular

development and corneal stroma maintenance.

3.3 Processed Amniotic Fluid (pAF): Preliminary Clinical Data

The presence of peptides in processed amniotic fluid (pAF) that have roles in ocular development and corneal stroma maintenance, along with the understanding that one of the in utero beneficial functions of AF is to bathe the fetuses eyes, led us to hypothesize that pAF may be a valuable treatment regimen to improve corneal re-epithelialization following PRK.

Our pAF has been clinically used in over 2000 applications for over 100 different conditions. A majority of treatments have been for wounds and burns with 3 patients receiving pAF for the treatment of ocular GVHD. No adverse events have been directly associated with the injection of pAF or when pAF has been topically applied for the treatment of ocular GVHD.

For the 3 patients treated for ocular GVHD at the University of Utah, each patient received a dose of 0.5 ml per eye daily in 2 divided doses, and no toxicities were observed. One patient with severe dry eye had a good partial response with a decrease in the need for artificial tears and the use of PROSE lenses. A second patient had stabilization of the disease after discontinuation of all immunosuppression. The third patient reported no change.

4 Eligibility Criteria

Inclusion Criteria:

1. Patients aged 21 years and older.
2. Patients undergoing PRK for visual correction in both eyes.
3. Willing and able to give consent for study participation and comply with study procedures, including follow-up visits.

Exclusion Criteria:

1. Patients with any active eye disease, including keratoconus or any other ectatic disorders.
2. Patients with documented uncontrolled diabetes.
3. Patients with severe dry eye as measured by corneal staining.
4. Patients with calculated PRK treatment resulting in residual stromal bed <300 um.
5. Patients who have had previous eye surgery or refractive laser procedures.

6. Patients with any active collagen vascular disease.
7. Patients who do not have potential of 20/20 or better best-corrected vision in each eye.

5 Study Design and Procedures

This is a randomized, double-masked, placebo-controlled study to evaluate the safety of using pAF in patients following PRK.

Pre-operatively each patient will be randomized to one of two post-operative drop regimens. Neither the patient nor their doctors will know if they are receiving pAF or placebo. The vials containing pAF and placebo (NaCl 0.9%, Baxter Medical) will be packaged the same by the Cell Therapy and Regenerative Medicine (CTRM). The assigned drop will be administered in both eyes throughout the study.

Regimen 1 will serve as the placebo control. For the first week only, patients in this regimen will receive placebo saline solution (NaCl 0.9%, Baxter Medical) for use four times daily. Patients will otherwise be treated with our standard post-operative drop regimen, which includes prednisolone acetate 1% suspension (4x/day for 7 days, then 2x/day for 2 additional weeks), moxifloxacin 0.3% (4x/day for 7 days), and ketorolac 0.5% (2x/day for 3 days only). The prednisolone acetate will be tapered to fluorometholone 0.1% suspension (3x/daily on days 22-60 then 2x/daily on days 61-90). A bandage contact lens will also be placed following surgery as is standard care for PRK patients.

Regimen 2 will have a bandage contact lens placed post-PRK and have an identical drop regimen with the exception of replacing the placebo saline with pAF four times daily for one week.

All patients will be instructed to use supplemental preservative free artificial tears from individual vials (any brand) no less than 3 but up to 8 times a day in both eyes the first week. After the first week, they will continue to be allowed use of preservative free tears as needed per the standard post PRK regimen in our center.

Patients are instructed to use oral medications as needed post-surgery. Ibuprofen or naproxen may be helpful in preventing pain for the first 3 days following the procedure. Patients will also be prescribed hydrocodone-acetaminophen 5-325 mg every four hours as needed for breakthrough pain. Patients will record how many pain pills are taken each day on a worksheet provided by the research team after the surgery.

The patients will have a pain rating sheet and will be asked to grade their peak subjective pain on a scale of 0 to 10 (with 10 being the most painful) for the first 7 days. They will grade each eye separately.

The day of surgery will be designated day 1, as surgery occurs in the early morning. The size of the epithelial defect created by PRK will be measured at the time of surgery completion.

Surgeons will administer the first dose of masked study drug (placebo or pAF fluid) directly after surgery, the morning of day 1, and three more times that day. Patients will then administer drops four times a day total for the next 6 days, for a total of 7 days of study drug administration. The patients will begin filling out the pain survey the night of day 1.

At a designated time on day 1 (2nd visit post-surgery), 3, 4, 5, 6, 7, and 8 each patient will be examined by one of the study investigators who will be masked to the drop regimen. The investigator will grade the size of the epithelial defect on day 1(AM), 3, 4, 5, 6, 7, and 8 by measuring the largest horizontal and vertical meridians using slit lamp biomicroscopy. If a patient has re-epithelialized by an earlier exam day (i.e., day 3) they will be able to skip all subsequent in person examinations except for day 8 (i.e., skip days 4, 5, 6, and 7). All patients will still need to record their pain rating scale at the end of each day and return for the day 8 visit.

The study investigators will be masked to which drop is being used for each patient. Patients will be required to store all drops in the freezer and will be masked as to which type of drop is being used.

Patients will also be seen at post-operative months 1, 3, 6 and 12. At each of these visits visual acuity and manifest refraction will be checked, along with a measure of ocular surface staining and corneal regularity. These are all standard procedures performed for post-operative PRK patients regardless of study participation.

5.1 Schedule of Events

| | Baseline | Day of Surgery (Friday) | | Days after Surgery | | | | | | | | | | |
|--|----------|----------------------------|---|--------------------|--------|--------|--------|--------|---------------------------------------|----------------------------|----------------------------|-----------------------------|------------------------------|---|
| | | Day 1 (AM) | Day 1 (2 nd visit post- surgery) | Day 3 | Day 4* | Day 5* | Day 6* | Day 7* | Day 8 Friday AM (in-person visit)* | Month 1 (Day 30±10)* | Month 3 (Day 90±14)* | Month 6 (Day 180±30)* | Month 12 (Day 365±30)* | |
| Informed Consent | X | | | | | | | | | | | | | |
| Eligibility | X | | | | | | | | | | | | | |
| Medical History | X | | | | | | | | | | | | | |
| Concomitant medications ² | X | X | X | X | X | X | X | X | X | X | X | X | X | |
| Randomization ³ | | | X | | | | | | | | | | | |
| PRK Surgery | | | X | | | | | | | | | | | |
| Dispense Masked Study Drug ⁴ | | | X | | | | | | | | | | | |
| Study Drug Compliance ⁵ | | | | X | X | X | X | X | | | | | | |
| Pain Assessment ⁶ | | | | X | X | X | X | X | | | | | | |
| Size of Epithelial Defect ⁷ | | | X | | X | X | X | X | X | | | | | |
| Uncorrected VA ⁸ | X | | | | | | | | | X | X | X | X | X |
| Manifest Refraction | X | | | | | | | | | | X | X | X | X |
| Target Post-OP Refraction | X | | | | | | | | | | | | | |
| BCVA ⁸ | X | | | | | | | | | | X | X | X | X |
| Ocular Surface Staining | X | | | | | | | | | | X | X | X | X |
| Corneal Topography | X | | | | | | | | | | X | X | X | X |
| Ocular Adverse Events | | | | X | X | X | X | X | X | | X | X | X | X |

1. The pre-op screening/baseline visit may be performed in 2 separate visits.

2. Record systemic medications at baseline and any subsequent changes; Record start and stop dates of ocular medications prescribed as standard care post-PRK surgery, note any deviations from prescribed regimens.

3. Randomization to study drug assignment will occur when patient presents day of surgery.

4. First dose of study drug applied to each eye at completion of surgery. Three additional doses administered by patient on day of surgery, then 4x per day through Day 7.

5. Patient will document each use of study drug and oral pain medication in diary.

6. Patient will assess highest level of daily pain/discomfort at the end of each day.

7. Grade defect dimensions until healed.

8. Visual acuity will be measured on Snellen charts. Conversion to logMAR equivalents will be completed on the back end by the Biostatisticians.

* Study procedures may be performed via telehealth or by phone at the discretion of the treating provider.

Table 1: Schedule of Events

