6.1.9 Follow-up of Serious, Unexpected and Related Adverse Events

All serious, unexpected and related adverse events, that are unresolved at the time of the patient's termination from the study, will be followed by the site investigators until the events are resolved, subject is lost to follow-up, the adverse event is otherwise explained or has stabilized, or 12 months have passed from the time of last study dose.

7 Assessment of secondary endpoints

1. Re-epithelialization will be graded by trained, masked examiners on days 1, 3, 4, 5, 6, 7, and 8 unless patient re-epithelializes sooner in which case they can skip visits until day 8. Dimensions of the epithelial defects will be directly measured using slit lamp bio-microscopy. The baseline epithelial defect will be measured by surgeons on Day 1 at the time of surgery. Examiners will be masked as to which patients are using pAF vs. placebo. A vertical and horizontal measure of defect in mm will be performed, and defect area calculated. A complete re-epithelialization (absence of a defect) is defined when the measures equal zero.
2. Pain will be measured through a 0-10 scale on days 1, 2, 3, 4, 5, 6, and 7. Participants will rate their peak pain at the end of each day and directly return the forms at their in-person visit on day 8 to the examiners. They will complete a separate survey for each eye.
3. Uncorrected visual acuity will be measured at post-operative day 8, months 1, 3, 6, and 12 by trained physicians.
4. Manifest refraction and best-corrected visual acuity will be measured at months 1, 3, 6, and 12 by trained physicians.
5. Ocular surface staining will be measured at post-operative months 1, 3, 6, and 12 using an area density index.²⁵ This is a published and validated index used to measure corneal staining. Corneal regularity will also be measured at months 1, 3, 6, and 12 with the Surface Regularity Index (SRI) obtained via Zeiss Atlas 9000 Corneal Topography™.

8 Other Medications

- Oral pain medications usage will be tracked for the first 7 days.

9 Patient Withdrawal From Study

- A subject may withdraw their consent at any time without affect to their care.

10 Discontinuation of Study Drug

The study drug will be discontinued if any of the following occur:

- Development of severe ocular infection.
- Any other condition that in the opinion of the treating physician and ophthalmologist are not compatible with participation in this study.

11 Discontinuation of Study

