12.3 Statistical Power and Sample Size: Time to complete re-epithelialization

Time to complete re-epithelialization will be measured from the end of surgery until the date of the exam where complete re-epithelialization is observed. While evaluation times will be collected, since the time of surgery and the time of the follow-up exam are dependent upon scheduling, time to complete re-epithelialization will be analyzed as an integer, being simply the number of calendar days from the day of surgery to the date of the first examination demonstrating complete re-epithelialization.

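### Table 1 lets the examination visits on Days 4–8 and at Months 1–12 be held remotely, which contradicts the examination-based endpoints, and the SAP does not say how to code a remote contact

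*Protocol*

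**What the plan says.** Protocol 5.1, Table 1, marks visit columns with an asterisk: "Day 3 | Day 4* | Day 5* | Day 6* | Day 7" (Day 7 is starred too; Day 1 and Day 3 are not), and "Month 1 (Day 30±10)* | Month 3 (Day 90±14)* | Month 6 (Day 180±30)* | Month 12 (Day 365±30" (Month 12 also starred). The Day 8 header reads "Day 8 Friday AM (in-person visit", then a closing bracket and the same asterisk. The footnote is "Study procedures may be performed via telehealth or by phone at the discretion of the treating provider".

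Other sections define the outcomes by examination:

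- **Healing.** Protocol section 5 has the investigator grade the defect on Days 1, 3, 4, 5, 6, 7 and 8 "by measuring the largest horizontal and vertical meridians using slit lamp biomicroscopy". Protocol section 7 adds: "A complete re-epithelialization (absence of a defect) is defined when the measures equal zero". Protocol 12.3 and SAP 3.2.1 count "the number of calendar days from the day of surgery to the date of the first examination demonstrating complete re-epithelialization".
- **Acuity.** The SAP's secondary efficacy endpoint (3.2.2) is uncorrected acuity at Day 30. It is read on Snellen charts (Table 1, note 8) by trained physicians (protocol section 7).
- **Safety.** Protocol 5.4 rests the primary, safety endpoint on scheduled eye examinations on Days 1 to 8 and at Months 1, 3, 6 and 12. SAP 11.2 reports loss of best-corrected vision at 6 months and 1 year.

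SAP 10.1 assigns the midpoint of the possible times when visits are missed, and 9 days to eyes not healed by Day 8. Neither document mentions remote contacts in the analysis.

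**The concern.** Defect dimensions, chart acuity, refraction, staining and topography all need the patient in the clinic, yet the footnote lets any of the starred visits take place without one. A provider who follows Table 1 as written can lose the examinations that date healing without breaching the protocol. The analyst then has no rule saying whether a remote contact is an examination, a missed visit or missing data, so two analysts could assign different days to the same eye.

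Day 8 is the most awkward case. An eye last seen open whose Day 8 contact was by phone fits neither the 9-day rule nor the dropout rule clearly. Because remote use is left to the provider's discretion, it may also depend on how the eye is doing, so the gaps need not occur at random.

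**Working it through.** **Inputs.** From protocol 12.5 and SAP 6: means 3.1 and 3.6 days, effect 0.5 day, SD 0.5–0.7, ICC 0.5–0.75, 28 patients with two eyes each per arm. Two-sided alpha is 0.05 (protocol 12.1). The share of patients seen remotely is not in the documents and is varied as an assumption.

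**1. The plan's own table.** With two eyes per patient, SE = SD × √((1 + ICC)/28). At SD 0.6 and ICC 0.6, SE = 0.6 × √(1.6/28) = 0.143. The difference detectable with 80% power, using t with 54 df, is (2.005 + 0.848) × 0.143 = 0.41 day, as printed. Across all 18 printed differences, noncentral-t power is 78.5–80.2% (target 80%) and 88.9–89.8% (target 90%). The sample-size table is sound.

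**2. Where healing falls on the visit schedule.** Protocol section 5 states "The day of surgery will be designated day 1, as surgery occurs in the early morning", so 3.1 and 3.6 calendar days after surgery are about study Days 4.1 and 4.6. These are the first starred visits. With normal healing times rounded to the nearest day, an eye is first seen healed on Day 4 or later if its time exceeds 2.5 days:

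| Mean | SD | z = (2.5 − mean)/SD | Share on Day 4 or later |
|---|---|---|---|
| 3.1 | 0.6 | −1.00 | 84% |
| 3.1 | 0.7 | −0.86 | 80% |
| 3.6 | 0.6 | −1.83 | 97% |
| 3.6 | 0.7 | −1.57 | 94% |

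The result depends on how the cited study counted days. If its means are study-day numbers, the cut is 3.5 and the shares over SD 0.5–0.7 are 21–28% and 56–58%. If times are instead rounded up to the next day, the shares at SD 0.6–0.7 are 94–99.6%.

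**3. Effect of missed examinations.** Bilateral healing times were simulated with a patient random effect and rounded to the nearest day (at least 20,000 trials per setting). Arms were compared by a t-test on patient means, which is equivalent to the planned mixed model in balanced data. In a share of patients Days 4 and 5 are remote and Day 6 is the next slit-lamp examination. An eye open on Day 3 and closed on Day 6 could have closed on Day 4, 5 or 6, so the SAP midpoint is Day 5.

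| Patients affected | Power, SD 0.6 / ICC 0.6 | Mean difference (days) |
|---|---|---|
| 0% | 89% | 0.50 |
| 5% | 87% | 0.49 |
| 10% | 85% | 0.47 |
| 25% | 78% | 0.43 |
| 50% | 67% | 0.37 |

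The 89% is below the 93% that the step 1 formula gives for 0.5 day because whole-day recording adds variance. At SD 0.7 and ICC 0.75, power falls from 76% to 67% (25% affected) or 58% (50%).

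**4. Sensitivity to the pattern of remote visits**, at SD 0.6 and ICC 0.6. If only Day 4 is remote in 25% of patients, power is about 85–86%. If all of Days 4–7 are remote and Day 8 is the next examination, the midpoint is Day 6, and power is already about 70% with 10% of patients affected.

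**The case against.** A reader might infer that a healing day or an acuity can validly be recorded from a phone report. The documents do not support that. The footnote is permissive and redefines no endpoint; healing still requires measured dimensions of zero at an examination, and acuity still requires a chart and a physician. A phone contact satisfies neither. It would also be wrong to call healing time the trial's primary endpoint: that is safety, and healing time is the primary efficacy endpoint.

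The asterisk also has a sensible use. Protocol section 5 lets patients who have healed skip in-person examinations until Day 8, while medications, compliance, pain and adverse events are still due and can be collected by phone. That would explain stars on Days 4–7 and none on Day 3. It is an inference, though. The footnote is not limited to healed patients, and this reading explains neither Day 8 nor the month visits.

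Gaps are partly handled. SAP 10.1 has the midpoint rule, and SAP 10.2 offers a supportive analysis when Day 30 acuity is missing. SAP 10.1.1 adds a clustered log-rank test, but its triggers are non-compliance, eyes unhealed at Day 8 and dropout, not missed interim visits.

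The objection to the size also stands in part. The remote rate is unknown, and with few patients affected on Days 4–5 the loss is a few points.

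**Conclusion.** The contradiction is real and does not depend on any assumed rate. Table 1 permits remote conduct of visits whose scheduled measurements need an examination, Day 8 is both in-person and starred, and the SAP gives no coding rule. The primary efficacy endpoint, the secondary efficacy endpoint and the examination-based safety findings are all exposed; eyes closed on Day 3 are not.

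The cost is conditional. At SD 0.6 and ICC 0.6, with Days 4–5 remote and the midpoint rule, power goes from 89% to 87–85% if 5–10% of patients are affected, and to 78–67% if 25–50% are. These figures rest on normal healing times, rounding to the nearest day, planning means counted from surgery, and remote use unrelated to healing or arm. They measure the loss from missed examinations, so only keeping the examinations in person recovers it; a different analysis of the same gaps would not replace the lost observations.

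Should be fixed: the repair is small, and a missed examination cannot be recovered later.

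**What to change.** In protocol 5.1:

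- Limit the footnote to two uses: items that need no examination (adverse-event and medication queries, pain diary, compliance), and Day 4–7 contacts with patients already documented as healed at an in-person examination.
- Remove the asterisk from Day 8.
- State that defect size, acuity, refraction, staining and topography are in-person only.
- Record the mode of every visit in the data capture system.

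In SAP 10.1, add that a remote contact is never an examination and is handled as a missed visit under the existing midpoint rule. In SAP 10.1.1, add an interval-censored analysis as a sensitivity analysis only; making it primary would replace the planned mixed model.

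The cost is a rewritten footnote, one data field, one SAP sentence and one sensitivity analysis. Some remote contacts will then count as missed examinations.
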